## **8.9.2 Secondary Efficacy Analyses**

### **8.9.2.1 Secondary Efficacy Analyses at Primary Endpoint**

The secondary efficacy analyses will be made with ANOVA comparing change from baseline (visit 1) to the primary outcome timepoint (visit 13) of all the secondary measures. If the parametric assumptions for the ANOVA analyses are not met, the analogous nonparametric methods will be used (Kruskall-Wallis, Wilcoxon Rank-Sum).

Clinician Administered PTSD Scale-4 (CAPS-4) global scores will also be analyzed for effect size with the Cohen's *d* analysis.

Global Assessment of Functioning (GAF) total score will be analyzed in the same manner as the CAPS-4 global scale primary analysis.

Beck Depression Inventory-II (BDI-II) total score will be analyzed in the same manner as the CAPS-4 global scale primary analysis.

Post Traumatic Growth Inventory (PTGI) total will be analyzed in the same manner as the CAPS-4 global scale primary analysis.

Dissociative Experiences Scale-II (DES-II) total will be analyzed in the same manner as the CAPS-4 global scale primary analysis.

Pittsburgh Sleep Quality Index (PSQI) global scores will be analyzed in the same manner as the CAPS-4 global scale primary analysis.

NEO Personality Inventory (NEO PI) five factor scores will be analyzed in the same manner as the CAPS-4 global scale primary analysis.

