#### **6.1.1 Outcome Measures**

The primary outcome measure will be the CAPS, a clinician-scored measure for PTSD diagnosis and measure of symptom intensity and severity. The CAPS provides a means to evaluate the frequency and intensity dimensions of each symptom, impact of symptoms on the patient's social and occupational functioning, overall severity of the symptom complex and global improvement since baseline and the validity of the ratings obtained. The CAPS takes approximately one hour to complete. The CAPS interviews have been determined to have good internal consistency, concurrent validity, and test/retest reliability [78, 79]. An independent rater will assess all participants according to the Time and Events table.

The Global Assessment of Functioning (GAF) is a measure of global functioning and general function made through observations. The GAF consists of a single score, with scores ranging from 0 to 100, with 100 reflecting superior function and zero reflecting serious risk of causing harm to the self or others. The GAF will be recorded by the independent rater according to the Time and Events table.

The Beck Depression Inventory-II (BDI-II) is a 21-item a self-report measure of depressive symptoms [80] that will serve as a measure of depression. It takes five to ten minutes to complete. Participants will complete the BDI-II according to the Time and Events table.

The Post Traumatic Growth Inventory (PTGI) is a 21-item self-report measure of perceived growth or benefits occurring after a traumatic event. It contains five subscales; relationship to others, new possibilities, personal strength, spiritual change, and appreciation of life. In this study, participants will complete the PTGI in reference to the time since the trauma at baseline, but will respond in reference to the beginning of their participation in the study on all subsequent occasions. Participants will complete the PTGI according to the Time and Events table.

The DES-II is a 28-item self-report measure of dissociation, defined as a lack of normal integration of an individual's thoughts, feelings, or experiences into the stream of consciousness or memory [81, 82]. It is an established measure of dissociative symptoms. The scale consists of statements describing facets of dissociation. Respondents indicate how often the specific experience happens to them, from "never" to "always." Responses

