A blinded independent rater who will not be present during any of the therapy sessions will administer the CAPS and assess the participant on the GAF. To establish independent rater reliability, the investigators will have the option to video record the screening CAPS interview in as many instances as necessary. The C-SSRS will also be

administered at screening to assess suicide risk. Suicide risk will also be assessed via psychiatric interview. The Clinical investigator and independent rater will use medical records, communication with the participant's treating psychiatrist or therapist if applicable and psychiatric interview to assess potential risk to others. The participant will complete the BDI-II, PTGI (in reference to time since the trauma), PSQI, DES-II and NEO-PI. The entire visit should take between 1.5 and 2.5 hours. Screening may take place over more than one day and up to four months prior to Visit 1 (enrollment). The participant may also have the first preparatory session (Visit 2) prior to enrollment.

If eligibility is confirmed, the participant will be enrolled and will be issued a subject number and contacted to schedule introductory non-drug psychotherapy sessions and first experimental session. Any participant who must discontinue a medication will, after consultation with the prescribing physician, be given a schedule to begin tapering off that medication so washout will be completed before the first experimental session, with the interval between the start of washout (the last day the medication was taken) and the first experimental session being at least five times the drug and active metabolites' half-life, plus one week for stabilization. The first experimental session will be scheduled to occur after washout is complete, if applicable.

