## 6.2.7 Evaluation at Primary Endpoint & Unblinding (Visit 13)

The primary endpoint evaluation in Stage 1 will occur one month after the second blinded experimental session. This visit will consist of two meetings that may be completed on separate days, one with the independent rater and the other with the therapists. The blinded independent rater will administer: CAPS to assess PTSD symptoms, BDI-II to assess depression symptoms, GAF to assess general psychological function, PTGI to assess post-traumatic growth (in reference to start of the study), PSQI to assess sleep quality, DES-II to assess dissociation symptoms and NEO PI to assess personality. The blinded independent rater will provide their belief of the subject's condition assignment.

After completing all assessments and measures with the independent rater, the subject will meet with the therapists for approximately 30 minutes. Following the visit with the independent rater the blind will be broken for the subject's condition assignment. The independent rater will remain blind to condition assignment at this time. The therapists will assess suicidality with the C-SSRS. The visual analog scale will be used to collect

changes in subjects who have pre-existing tinnitus and chronic pain symptoms.

If the subject had been assigned to receive medium dose or low dose MDMA, the therapists will discuss continuation to Stage 2. Low and medium dose subjects will not complete the third experimental session and associated integrative sessions in Stage 1. Participants who decline continuing to Stage 2 will complete the Responses to Research Participation Questionnaire (RRPQ). If participants had been assigned to the full dose condition in Stage I, they will provide their perceptions of experimental sessions at this point. The therapists will discuss scheduling the third open label full dose experimental session and integrative sessions.

Adverse Events and medications will be collected as described in Sections 8 and 9 of the protocol.

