### 6.2.12 Evaluation 12 Months after Final Experimental Session

All participants who completed Stage 1 only will be evaluated 12 months after their third experimental session, and all participants who completed Stage 2 will be evaluated 12 months after their third open-label MDMA-assisted psychotherapy session. The independent rater will administer the CAPS and assess participants on GAF, and participants will complete the PTGI (in reference to the start of the study), BDI-II, PSQI, DES-II and NEO PI. Suicidality will be assessed with the C-SSRS. Participants will also complete a questionnaire assessing positive and negative long-term effects of the study. Outcome measures will either be completed over the telephone or at the study site. A researcher who is a part of the study team may ask the subject questions about positive or negative effects about the study in person or on the phone and the participant will return self-report questionnaires in envelopes supplied by the investigators with the study site listed both as the mailing and return address. The visual analog scale will be used to collect changes in subjects who have pre-existing tinnitus and chronic pain symptoms. Subjects will complete the termination visit at this time.

Adverse Events and medications will be collected as described in Sections 8 and 9 of the protocol.

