### 8.5 Baseline Values

Baseline values are from screening/baseline visit for all measures, except C-SSRS. For C-SSRS, pre-enrollment scores will be used as a measure of ‘lifetime’ suicidal ideation and behavior, and preparatory session 2 (visit 3) pre-drug Since Last Visit C-SSRS scores will be used as ‘baseline.’ If a subject was not administered the C-SSRS at preparatory session 2 (visit 3), then ‘baseline’ scores will be from preparatory session 3 (visit 4).

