#### Long-term Follow-up

For the CAPS, PTGI, BDI-II, GAF, PSQI, DES-II, and NEO PI, the absolute changes in the measures from baseline to the long-term follow-up visit (one year post final experimental year) will be compared with t-tests. The absolute changes in the measures from long-term follow-up to End of Stage 1 (visit 18, 125 mg) or long-term follow-up compared to End of Stage 2 (visit 33, 30 and 75 mg) will be compared with within-subject t-tests.

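### PTGI is asked about growth since the trauma at baseline and since study start afterwards, so the planned PTGI change from baseline is not a change in growth

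*SAP*

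**What the plan says.** Protocol 6.1.1 sets two reference periods: "participants will complete the PTGI in reference to the time since the trauma at baseline, but will respond in reference to the beginning" of study participation on all later occasions. The visit descriptions repeat this. Protocol 6.2.1, for baseline, says "The participant will complete the BDI-II, PTGI (in reference to time since the trauma), PSQI, DES-II and NEO-PI". Protocol 6.2.7, for Visit 13, lists "PTGI to assess post-traumatic growth (in reference to start of the study". Sections 6.2.8, 6.2.10 and 6.2.11 use the study-start reference at Visit 18, the secondary endpoint and the end of Stage 2. Section 6.2.12 does so at 12 months: "participants will complete the PTGI (in reference to the start of the study), BDI-II, PSQI, DES-II and NEO PI".

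The SAP makes no exception for PTGI. Section 8.5 states "Baseline values are from screening/baseline visit for all measures, except C-SSRS". Section 8.9.2.1 applies ANOVA "comparing change from baseline (visit 1) to the primary outcome timepoint (visit 13) of all the secondary measures", and specifically "Post Traumatic Growth Inventory (PTGI) total will be analyzed in the same manner as the CAPS-4 global scale primary analysis". The CAPS-4 analysis in 8.9.1 is of a baseline-to-Visit 13 difference score. Under Long-term Follow-up in 8.9.2.2, PTGI is among the measures for which "the absolute changes in the measures from baseline to the long-term follow-up visit" are to be compared with t-tests. Section 3.2 of both documents describes the PTGI objective as a change in posttraumatic growth from baseline, and protocol 12.0 also compares change in PTGI between dose conditions.

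**The concern.** Protocol 6.1.1 describes PTGI as a measure of perceived growth following an event, so each score is already growth since a stated reference point. The later score alone describes growth since study start. Subtracting an answer about a different and usually much longer period removes growth that preceded the study; it does not adjust for a starting level. A subject who reports clear growth during the study, but had reported still more since the trauma, is recorded as declining.

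The quantities at stake are the PTGI change means by arm, the baseline-to-12-month test, and any PTGI effect size built on the change. The last matters because SAP section 6.0 gives supplying effect sizes for later studies as a purpose of this pilot.

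**Working it through.** The documents state no PTGI power, SD or effect size, so there is no figure to reproduce. The check has two parts: what the change score measures, and how far this could move results.

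**1. What is subtracted**

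| Comparison (SAP) | Earlier score refers to | Later score refers to | Same reference? |
|---|---|---|---|
| Baseline to Visit 13 (8.9.2.1) | trauma | study start | No |
| Baseline to 12 months (8.9.2.2) | trauma | study start | No |
| Visit 13 to Visit 18 (8.9.2.2) | study start | study start | Yes |
| Visit 13 to Visit 28, crossover (8.9.2.2) | study start | study start | Yes |
| Visit 28 to Visit 33 (8.9.2.2) | study start | study start | Yes |
| Visit 18 or 33 to 12 months (8.9.2.2) | study start | study start | Yes |

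Let S be the since-trauma score and G the since-study score. The planned change is G − S, with mean E(G) − E(S). Its sign depends on growth before the study. For example, with mean G = 1 SD, mean S = 2 SD gives a change of −1 SD, mean S = 1 SD gives 0, and mean S = 0.5 SD gives +0.5 SD.

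**2. Between arms at Visit 13**

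Randomisation gives S the same expected value in every arm, so the arm difference in G − S has the same expectation as the arm difference in G. Assume equal SDs and correlation r between S and G. Relative to Var(G):

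- change score: 2(1 − r)
- G with S as covariate: 1 − r²
- covariate form relative to change score: (1 − r²) / [2(1 − r)] = (1 + r)/2, which never exceeds 1

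Results for a three-arm ANOVA with 12, 6 and 6 subjects, two-sided alpha 0.05 and full dose better by 1 SD (an assumed effect):

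| r | Variance, change | Variance, covariate | Power, change | Power, G alone | Power, G with covariate |
|---|---|---|---|---|---|
| 0 | 2.0 | 1.00 | 0.29 | 0.52 | 0.50 |
| 0.2 | 1.6 | 0.96 | 0.34 | 0.52 | 0.51 |
| 0.5 | 1.0 | 0.75 | 0.52 | 0.52 | 0.62 |
| 0.7 | 0.6 | 0.51 | 0.75 | 0.52 | 0.80 |

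With no dose effect and a common gap of −0.5 SD between the two answers, the simulated type I error of the change-score ANOVA was 0.047 to 0.050.

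**3. Baseline to 12 months, taken as a paired test**

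The SD of the difference is √[2(1 − r)] and the noncentrality is gap × √n / √[2(1 − r)]. The probability that the gap between the two answers is declared a change, for r from 0 to 0.7, is:

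| Gap in means | n = 6 | n = 12 | n = 24 |
|---|---|---|---|
| 0 | 0.05 | 0.05 | 0.05 |
| 0.25 SD | 0.07–0.10 | 0.09–0.18 | 0.13–0.33 |
| 0.5 SD | 0.11–0.25 | 0.20–0.53 | 0.38–0.86 |
| 1 SD | 0.29–0.72 | 0.61–0.98 | 0.91 to >0.99 |

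The sample sizes are one comparator arm, the full-dose arm, and all 24 subjects.

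**The case against.** The best defence is that the Visit 13 analysis is a randomised comparison of dose groups. Both documents frame the objective that way, and the comparison stays valid despite the mixed reference periods. That is right: for this test the problem is the reading of the arm means, not the error rate.

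The 12-month test is not clearly specified either. SAP 8.9.2.2 calls only the comparison with the end of stage within-subject, so the baseline comparison could be between groups, and a gap common to all groups would then cancel. This also stands: the probabilities in part 3 apply only to a paired reading. On either reading, the values are still not change in growth.

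The variance and power comparison in part 2 applies to any change score and is not in itself evidence of harm from the mismatch. It shows what replacing the subtraction does to precision. Comparing Visit 13 scores alone would lose power when r exceeds 0.5 (0.52 against 0.75 at r = 0.7). The covariate form meets that objection, because it is at least as precise as subtraction at any r, apart from one degree of freedom.

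The effect-size point is conditional. The SAP specifies Cohen's d only for CAPS-4, and protocol 12.0 promises effect sizes for all outcomes without saying that they come from change scores. Finally, this is one secondary measure in a pilot, and no primary or safety conclusion depends on it.

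**Conclusion.** The concern holds. PTGI change from baseline, as planned, mixes two reference periods and does not measure the stated objective. The mismatch is explicit in the text and needs no assumption. It affects the Visit 13 change means by arm, the baseline-to-12-month change, and any effect size computed from these.

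The size of the effect cannot be fixed from the documents. The gap between the two answers, their SDs and their correlation are not given, so the figures above are ranges under equal SDs and r from 0 to 0.7, and the direction of the mean change is unknown. The point should be corrected before analysis, but it is confined to one secondary measure.

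**What to change.** - **SAP 8.9.2.1:** for PTGI, compare the Visit 13 total (reference: study start) directly between dose groups. Do not subtract the since-trauma score. Report that score descriptively, and state in the SAP beforehand whether it enters as a covariate; including it protects precision if r turns out to be high. Compute any PTGI effect size at Visit 13 from the since-study score.
- **SAP 8.9.2.2, Long-term Follow-up:** remove PTGI from the baseline-to-follow-up t-test and summarise the 12-month since-study score itself.
- **Keep unchanged:** the PTGI contrasts between post-baseline visits, namely Visit 13 to 18, Visit 13 to 28 in crossover subjects, Visit 28 to 33, and Visit 18 or 33 to 12 months.
- **Wording:** align the PTGI objective in section 3.2 of both documents, and the reference to change in PTGI in protocol 12.0.

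The cost is a few lines in the SAP and a matching text revision in the protocol. No new data, visits or instruments are needed.

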### **8.9.2.2 Secondary Efficacy Analyses at Secondary Endpoints**

#### Assess 3 vs. 2 experimental MDMA sessions

For the CAPS, PTGI, BDI-II, GAF, PSQI, DES-II, and NEO PI, the absolute changes in the measures from the primary endpoint to end of Stage 1 for the 125 mg group will be compared with t-tests. In the crossover subjects (30 mg and 75 mg group) the absolute

changes in the measures from the secondary endpoint to end of Stage 2 will be compared with t-tests.

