## 2.0 Background Information

#### 2.1 Introduction

The Multidisciplinary Association for Psychedelic Studies (MAPS) is a non-profit research and educational organization working to obtain approval for the prescription use of 3,4-methylenedioxymethamphetamine (MDMA)-assisted psychotherapy in patients with posttraumatic stress disorder (PTSD).

Encouraging data has been obtained and submitted to the FDA from MAPS' recently completed United States (U.S.) pilot study, IND #63-384 (MP1). MAPS is currently sponsoring another Phase 2 study in Switzerland. An additional Phase 2 study is planned to start in the near future in Canada, with approval from Health Canada and a Canadian Institutional Review Board (IRB) already obtained. Ongoing and planned Phase 2 studies, along with the study described in this protocol, are laying the groundwork for an eventual End-of-Phase 2 meeting with FDA and possible Phase 3 multi-site MDMA/PTSD research studies.

The proposed pilot study will examine the safety and efficacy of MDMA-assisted psychotherapy in twenty-four veterans, firefighters or police officers with service related PTSD, and will seek to enroll roughly equal numbers of men and women. This study will include those with chronic PTSD of at least six months duration who satisfy PTSD diagnostic criteria despite having received prior treatment with either medication or psychotherapy. Full, medium and low dose MDMA will be assessed in Stage 1, as well as the benefit of three vs. two full dose sessions. Subjects who received the medium and low dose during Stage 1 will have the opportunity to cross over and take part in a second study segment, referred to as Stage 2, with three open-label experimental sessions. Stage 2 will be used to explore the optimal therapeutic dose of MDMA using a clinical titration dosing strategy.

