### 12.0 Data Analysis

The Sponsor will judge the clinical and statistical significance of the study and estimate effect size and statistical power based on a comparison of observer-blind data collected at baseline and the primary endpoint using the primary outcome measure, which is the CAPS.

The sample selection is expected to produce acceptably homogeneous groups due to their diagnosis of with PTSD with CAPS scores of at least 50 who have not responded to treatment. There is no expectation that conditions will differ significantly in composition by gender, race or ethnicity, duration of PTSD diagnosis or presence versus absence of other permitted psychiatric disorders, as depression.

The sponsor will examine individual CAPS, BDI-II, PTGI, PSQI, DES-II and GAF scores at baseline and the primary endpoint, in low dose, medium dose and full dose conditions. Descriptive statistics will be calculated for all measurements overall and by condition. Distributional characteristics will be examined for outliers and extreme values and, if either is evident. If outliers are found in primary or secondary outcome measures, the sponsor will perform analyses with and without the outlying data. Effect sizes for all outcome measures for primary endpoint, Stage 1, secondary endpoint, end of Stage 2, and 12-month follow-up will be estimated using Cohen's techniques.

All analyses of data from the primary endpoint will contain blinded data. Analysis of variance will be used to compare Global CAPS scores by dose condition at the primary endpoint.

Analysis of variance, or nonparametric analysis if assumptions are not met, will be used to compare the dose conditions for change in BDI-II, PTGI, PSQI, GAF, DES-II and NEO PI scores separately. If scores cannot be examined sufficiently in this model, then analyses will compare available data through the use of difference scores.

The sponsor will examine open-label data collected two months after the third Stage 1 experimental session. The sponsor will perform a within-subject analysis of full dose participants.

Subjects who discontinue treatment prior to the primary endpoint will be asked to complete an outcome assessment prior to continuing to the long-term follow-up. The data from these subjects will be tested for equivalence to data from subjects completing the study per protocol. If found to be equivalent, data from these subjects will be presented as

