When each subject completes the evaluation at the primary endpoint, the blind will be broken for that subject. Subjects who had been assigned to receive low dose or medium dose MDMA will subsequently have the opportunity to enroll in the open-label study arm, or “Stage 2.” Stage 2 must start within a maximum of 5 months after the subject finishes Stage 1. The open-label study arm will follow a similar sequence of events and procedures, except that there will be a single preparatory session, and all three MDMA-assisted psychotherapy sessions will be open-label. Subjects will receive an initial dose of 100 mg MDMA in the first experimental session, and one of two active doses of MDMA that are clinically titrated by the CI during the second and third open-label experimental sessions that will otherwise follow the same sequence of events (See Time and Events Table). Outcome measures except for the NEO PI will be repeated one month after the second Stage 2 experimental session, and all outcome measures will be repeated at the end of Stage 2.

The study will conclude with a one-year follow-up occurring 12 months after the final experimental session of Stage 1 for subjects who received full dose MDMA or who elected not to enroll in Stage 2 after receiving either the medium or low doses in Stage 1. Subjects who enrolled in Stage 2 will have their final follow-up 12 months after the final open-label experimental session. Outcome measures will be repeated at the 12-month follow-up, as well as a questionnaire concerning self-reported long-term effects of study participation.

Sub-studies in a select group of subjects in this study may be conducted for exploratory purposes. Subjects will complete a separate consent process if they chose to participate in these studies.

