| Perception of Third Session             |                |   |                  |                  |                  |                  |                  | X N |                  |                  | X N |
| RRPQ                                    |                |   |                  |                  |                  |                  |                  |                |                  |                  | X H |

A =First Integrative session is 1 day after exp session B = At least 24 hrs prior to 1st exp. session C =Approximately 6 hours post MDMA D =At the beginning of the session E =As needed F=Approximately every 60 minutes G =Given on 2nd preparatory session after meds are tapered (V3) H = Only for subjects starting Long term Follow up and not going to Stage 2 I =For 7 days post Exp. Session, C-SSRS D2 and D7 of calls only, General well being for all 7 days J =Subjects in the medium or low dose group will not have visits 14-18, but will instead move onto Stage 2. K= On the day of the 1st integrative session following the Exp. Session L=CAPS may be videotaped M=First preparatory session (V2) may happen at the time of screening, before enrollment. N= Full dose subjects only. O= Only in subjects with pre-existing tinnitus and/or chronic pain.

| Table 4.1: Stage2 Time & Events            | Preparatory                        | Experimental Session 1 |                         | Experimental Session 2 |                         |                              | Experimental Session 3 |                         | Follow-Up                                 | Long Term Follow-Up                               |
|--|------------------------------------|------------------------|-------------------------|------------------------|-------------------------|------------------------------|------------------------|-------------------------|---|---|
|  |                                    | V19*                   | V20                     | V 21,22,23             | V24                     | V 25,26,27                   | V28                    | V29                     |   |   |

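### The three-versus-two-sessions analysis is an uncontrolled before/after change: it cannot separate a third session from elapsed time, and its NEO PI component cannot be computed

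*SAP*

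**What the plan says.** Protocol 2.1 says that Stage 1 will assess the three dose levels, "as well as the benefit of three vs. two full dose sessions". SAP 2.0 repeats this. SAP 8.9.2.2, under secondary efficacy, carries the heading "Assess 3 vs. 2 experimental MDMA sessions" and names CAPS, PTGI, BDI-II, GAF, PSQI, DES-II and NEO PI. For the full-dose group it plans t-tests on the change between the primary-endpoint visit and the final Stage 1 visit. For the crossover subjects, the "changes in the measures from the secondary endpoint to end of Stage 2 will be compared with t-tests". Protocol 12.0 describes the full-dose part this way: "The sponsor will perform a within-subject analysis of full dose participants".

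The parent objective (Protocol 3.2 and SAP 3.2) is listed among exploratory analyses meant to inform protocol design. It compares scores before and after the third session in those who receive one, and it does not name NEO PI.

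**The concern.** A claim about three sessions versus two needs to show what would have happened after two sessions by the time the third is evaluated. The plan has no such observation. Each subject's own score after session 2 is a starting point for measuring change, not a control for the passage of time.

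SAP 8.0 treats p of 0.05 or less as statistically significant for all tests, and SAP 8.9.2.2 files this test under secondary efficacy. A significant result under the present heading would naturally be read as evidence that a third session adds benefit. Protocol 6.1.3 says that the sponsor wants to judge the therapeutic value of that session, so the reading matters for later protocols. The error can also run the other way: drift toward worsening over the interval would hide a real benefit.

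**Working it through.** The documents give no sample size, SD or effect size for this analysis, so there is no planned figure to reproduce. The check has four parts.

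**1. Is there a two-session comparator?**
- Stage 1: all full-dose subjects are planned to have session 3 (Protocol 5.0). Footnote J of the Stage 1 Time and Events table says of the others: "Subjects in the medium or low dose group will not have visits 14-18, but will instead move onto Stage 2".
- Stage 2: SAP 4.0 says "all three MDMA-assisted psychotherapy sessions will be open-label". No subset is planned to stop at two.
- So neither stage has a concurrent comparator.

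**2. What else differs between the two measurements?**
- *Follow-up.* "The primary endpoint evaluation in Stage 1 will occur one month after the second blinded experimental session" (Visit 13). The end-of-Stage-1 evaluation (Visit 18) is two months after session 3 (Protocol 6.2.8). Stage 2 has the same one-month and two-month pattern (Visits 28 and 33).
- *Interval, Stage 1.* Take 1 month = 4.35 weeks. Session 3 is 3 to 5 weeks after session 2, so Visit 18 falls 3 + 8.70 = 11.7 to 5 + 8.70 = 13.7 weeks after session 2. Subtracting 4.35 gives 7.3 to 9.3 weeks between Visits 13 and 18. If session 3 follows Visit 13, as unblinding at that visit implies, the range is 8.7 to 9.3 weeks.
- *Blinding, 125 mg group.* The blind is broken for each subject at Visit 13 (SAP 4.0), so subjects and therapists know the allocation by Visit 18. Protocol 6.2.7 keeps the independent rater blind at that point. The rater scores CAPS and GAF. BDI-II, PTGI, PSQI and DES-II are self-report (Protocol 6.1.1), so knowledge of allocation bears most directly on those four.
- *Crossover group.* Both time points are open-label, so no blinding is lost between them. The dose is decided separately for sessions 2 and 3 (Protocol 4.3 and 6.2.10), so session number can be mixed with dose. These subjects also had two blinded sessions in Stage 1.

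**3. How large a change reaches significance?** Two-sided paired t-test, alpha 0.05, n = 12 (the most available, since subjects lost after the primary endpoint are not replaced; Protocol 6.3):

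critical mean change = t(0.975, 11 df) × SD / √12 = 2.201 × SD / 3.464 = 0.64 SD.

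| Assumed SD of CAPS change | Observed mean change giving p = 0.05 |
|---|---|
| 10 | 6.4 |
| 15 | 9.5 |
| 20 | 12.7 |
| 25 | 15.9 |

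These are observed means. For a true drift δ (in SDs of the change score) and no effect of session 3, the rejection rate comes from the noncentral t with 11 df and noncentrality δ√12:

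| Assumed true drift (SD) | Rejection rate |
|---|---|
| 0 | 5.0% |
| 0.2 | 9.7% |
| 0.3 | 15.8% |
| 0.5 | 35.3% |

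The SDs and drifts are assumptions.

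**4. Can every listed test be computed?** The Stage 1 schedule has NEO PI at screening and Visit 13, not at Visit 18; Protocol 6.2.8 also omits it there. In Stage 2, SAP 4.0 excludes it from the assessment one month after session 2, and the schedule agrees. Each NEO PI contrast therefore lacks one of its two time points.

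**The case against.** The strongest reply is that the plan largely discloses what this is. Section 3.2 of both documents calls the objective exploratory and describes a before/after comparison in subjects who receive a third session. Protocol 12.0 calls the data open-label and the analysis within-subject. The study is a pilot, no decision rule hangs on the test, and subjects' perceptions of the third session are collected separately. This stands as a reason for modest severity. It does not remove the claim in the two introductions and the SAP heading, or the placement under secondary efficacy. A small sample makes an estimate imprecise; a missing comparator means that the contrast is not estimated at all.

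Three stronger readings are tempting, and the documents do not support them.
- *That Visit 18 is wholly unblinded.* The rater is formally kept blind at the primary endpoint. A rater might infer the dose because only full-dose subjects have Visit 18, but the documents do not say that this happens. Nor does a loss of blinding between measurements apply to crossover subjects.
- *That the three extra integrative sessions are a confounder.* Three follow every experimental session by design (SAP 4.0), so they belong to what a further session means here.
- *That 9.5 CAPS points measures the bias.* It is a critical value at one assumed SD, and nothing in the documents shows that drift of that size will occur.

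**Conclusion.** Wrong as written: the documents claim a property that the design lacks. The analysis can describe change after a third open-label session. It cannot show the benefit of three sessions over two, because there is no concurrent two-session group and follow-up is one month in one case and two in the other. That conclusion needs no numerical assumption. The size of any misattribution is unknown; the 0.64 SD threshold follows from n = 12, and its translation into CAPS points rests on the assumed SDs. The NEO PI mismatch is definite and can be checked against the schedules. None of this implies that a third session lacks benefit, only that this test cannot tell.

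**What to change.** In SAP 8.9.2.2, retitle the analysis *change after a third open-label session (uncontrolled, exploratory)*, in line with SAP 3.2. State that it is a paired within-subject analysis, reported as mean change with a 95% CI; the present text does not say paired, although other parts of the same section specify within-subject tests. Drop NEO PI from this test. Amend Protocol 2.1, SAP 2.0 and the SAP heading so that they no longer claim to assess the benefit of three versus two sessions.

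The cost is wording only. No visit, treatment or data collection changes, and the stated claim becomes weaker. A concurrent comparator is not a realistic remedy at this size: splitting the 12 full-dose subjects 6:6 would give 80% power only for a standardised difference of about 1.80 (two-sided 0.05, noncentral t with 10 df).
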